6. STATISTICAL EVALUATIONS

6.1 Reporting Conventions

Descriptive statistics will be presented for continuous and categorical variables. For continuous variables, number of observations (n), mean, standard deviation (SD), median, interquartile range (IQR), range, minimum (min) and maximum (max) will be presented. Frequencies and percentages will be presented for categorical variables. All descriptive statistics will be rounded to 2 decimal places.

6.2 Data Sets Analyzed

Two study populations are intention-to-treat (ITT) population and per-protocol (PP) populations which are defined in section 5.3.1.

The efficacy evaluations will be performed on both of the ITT and PP datasets while the safety evaluations will be performed on the ITT dataset. The primary conclusion will be made for the primary endpoint on the ITT population. Demographic and baseline (Visit 2) characteristics will be performed on the ITT population.

Sample size, mean, 95% confidence interval of mean, median, standard deviation, inter-quartile range, maximum and minimum will be summarized for continuous variables. For categorical variables, the frequency and percentage will be provided.

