8.3 Analysis of Efficacy and Safety

The efficacy measures are conducted on the per-protocol (PP) and intent-to-treat (ITT) basis. The per protocol will be defined as (1) The drug compliance is at least 80% (2) Subjects have completed data to determine the primary endpoint. (3) Subjects cannot have major protocol deviation. The major protocol deviation will be defined as (1) Inclusion or exclusion criteria not satisfied. (2) Not permitted concomitant medications (3) Wrong randomized treatment prescribed. An intent-to-treat (ITT) basis will be defined as the data are analyzed by the treatment groups to which the randomized patients who take at least one dose of study medication and have any post-baseline safety data collected. The safety measures are conducted on the patients who take at least one dose of study medication. The data are analyzed utilizing the last observation carried forward (LOCF) technique to impute the missing data.

The efficacy and safety information recorded on CRF will be summarized by tables presented in frequency and percentage for categorical variables, in mean with SD as well as median with the minimum and maximum for continuous variables. The comparison between three groups will be analyzed by nonparametric method as appropriate. All adverse events will be summarized with coding term, severity, relationship to study drug by frequency tables with the counts and percentage. In addition, serious adverse events will be listed with event narration.

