5.3 Statistical Methods Planned in the Protocol and Determination of Sample Size

5.3.1 Populations for Analysis

The INTENT-TO-TREAT (ITT) POPULATION consists of all randomized subjects who receive at least one dose of study medication and fulfill all inclusion, exclusion criteria and have any post-baseline safety data collected.

The PER-PROTOCOL (PP) POPULATION is defined as (1) The drug compliance is at least 80% (2) Subjects have completed data to determine the primary endpoint. (3) Subjects cannot have protocol deviation. The protocol deviation will be defined as (1) Inclusion or exclusion criteria not satisfied. (2) Not permitted concomitant medications (3) Wrong randomized treatment prescribed.

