6.7 Analysis of Safety

6.7.1 Adverse events (AEs)

The coding system used will be the Medical Dictionary for Regulatory Activities (MedDRA).

Pre-treatment AE is the AE onset before the first dosing of study drug, while treatment-emergent AE is the one onset after the first dosing of study drug. Pre-treatment AE and treatment emergent AE will be analyzed separately.

Frequency table of subjects with pre-treatment AE (PTAE) and treatment emergent AE (TEAE) will be presented by center and treatment.

For TEAE, adverse event incidents will also be summarized descriptively by system organ class and preferred term using MedDRA. If more than one type of event occurred within a system organ class/ preferred term for the

subject, the subject is counted only once for each system organ class/ preferred term.

For TEAE, incidence tables of severity, action taken, relationship to study drug, outcome and serious AE or not will be presented by center, preferred term and treatment.

The frequency distribution of severity, action taken, relationship to study drug, and outcome of all AE events will be presented by center, and treatment.

6.7.2 *Serious adverse events (SAEs)*

Incidence of serious adverse event will be tabulated. Serious adverse events incidents will be summarized descriptively by center, system organ class/ preferred term, and treatment group.

6.7.3 *Laboratory data*

Descriptive statistics of original data and net changes in hematology and biochemistry data will be presented by center, visit, and treatment.

Results of clinical significance with regard to laboratory data will be summarized with frequency and percentage.

6.7.4 *Physical Examination (PE)*

Incidence table including number and percentage of patient with abnormal PE will be tabulated by center, visit, and treatment for each body system.

The corresponding body system will be analyzed and reported using a transition table. The type of transition includes no change, change to normal, change to non-clinical significance, (NCS), change to clinical significance (CS) for each body system from baseline (Visit 2).

6.7.5 *Vital Signs*

Descriptive statistics of net changes in vital signs including systolic and diastolic blood pressure, heart rate and body temperature will be presented by center, visit, and treatment.

Results of clinical significance with regard to vital sign will be summarized with frequency and percentage.

6.7.6 *ECG*

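### Safety is placed on the ITT dataset with no as-treated rule, so on the default reading a misdosed subject's safety data are reported under an arm whose treatment they did not receive

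*SAP*

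**What the plan says.** SAP 6.2 names two populations, ITT and PP, and no safety population. Efficacy is run on both, "while the safety evaluations will be performed on the ITT dataset".

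SAP 5.3.1 says who is in ITT: randomised subjects who "receive at least one dose of study medication and fulfill all inclusion, exclusion criteria and have any post-baseline safety data collected". It does not say whether they are grouped by randomised or received treatment.

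Protocol 8.3 does address grouping for ITT: "data are analyzed by the treatment groups to which the randomized patients who take at least one dose of study medication". The sentence is garbled, but its sense is analysis by randomised group. The same paragraph then gives safety its own basis: "The safety measures are conducted on the patients who take at least one dose of study medication". No grouping rule follows.

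Both documents list "Wrong randomized treatment prescribed" among the deviations that exclude a subject from PP. Neither attaches any other consequence to it.

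SAP 6.7.1 says the adverse event frequency table "will be presented by center and treatment", and the other safety outputs in SAP 6.7 are worded in the same general way. Neither document says whether that means assigned or received treatment.

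SAP 5.4 says the analysis follows the protocol. The only departure it lists is that between-arm tests are dropped because the study was terminated on the interim result.

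**The concern.** Efficacy by randomised arm protects the comparison that randomisation created. Safety asks a different question: what happened to people who took the drug. If a placebo-randomised subject took PDC-1421, counting that subject's events under placebo puts drug exposure into the comparator and tends to shrink a drug-placebo difference. A mix-up between the two active arms blurs the dose comparison in the same way. For safety, understating a difference is the less cautious error.

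The other planned outputs would probably not reveal such a subject. All arms take two capsules per pack, and the label describes brown capsules for all. The compliance and mean daily dose formulas in SAP 6.5 count units of study medication without separating active from placebo.

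**Working it through.** The plan states no figure on this point, so there is none to reproduce. The check is a reading of the texts followed by simple arithmetic.

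**1. The two documents side by side**

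| Item | Protocol 8.3 | SAP 5.3.1, 6.2, 6.7 |
|---|---|---|
| Who is in the safety analysis | Everyone with at least one dose | ITT: dosed, all eligibility criteria met, some post-baseline safety data |
| Grouping for ITT | By randomised group | Not stated |
| Grouping for safety | Not stated | By treatment, not defined further |
| Effect of wrong treatment | Excluded from PP | Excluded from PP |

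**2. What happens to a misdosed subject.** The subject leaves PP and stays in ITT if the other ITT conditions are met. SAP 6.2 then brings the subject into every safety table. The only grouping rule attached to ITT is the randomised one, so a programmer would by default use the assigned arm.

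**3. Size per subject.** Input: 23 planned per arm at stage I (Protocol 8.1, SAP 5.3.4). Stage I is the relevant size because SAP 5.4 reports termination. The number of misdosed subjects is not in the documents.

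Suppose x of 23 subjects in an arm have an event, and one of the x actually received another arm's treatment.
- By randomised arm the incidence is x/23. By treatment received it is (x − 1)/22.
- The difference is x/23 − (x − 1)/22 = (23 − x)/506.
- At x = 1 this is 22/506 = 1/23 = 4.3 points, the maximum. At x = 5 it is 18/506 = 3.6 points.
- The arm the subject belongs to, with y of 23 events, goes from y/23 to (y + 1)/24. That is a shift of (23 − y)/552, at most 1/24 = 4.2 points.

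For k such subjects in one arm the maximum is k/23:
- k = 0: 0
- k = 1: 4.3 points
- k = 2: 8.7 points
- k = 3: 13.0 points

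**4. Effect on a difference between arms.** Assume, for illustration only, that k subjects are exchanged each way between two arms of n for the whole course, with true event rates p1 and p0.
- Expected rates by randomised arm are ((n − k)p1 + k·p0)/n and ((n − k)p0 + k·p1)/n.
- Their difference is (1 − 2k/n)(p1 − p0).
- With n = 23 and an assumed true difference of 20 points, k = 1 gives 20 × (1 − 2/23) = 18.3 points, and k = 2 gives 20 × (1 − 4/23) = 16.5 points.

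These are whole-course figures. One bag is dispensed at each of visits 2 to 5, so a single wrong bag covers about 14 of 56 days and would usually matter less.

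**The case against.** The strongest reply is that the protocol already keeps safety separate from ITT. Protocol 8.3 introduces ITT as a basis for the efficacy measures and then bases safety on dosing, and SAP 5.4 says the analysis follows the protocol. On that view the SAP wording is loose and no one has decided to group safety by randomised arm. Three further points support it: the bag label carries a subject number and visit number, which guards against dispensing errors; safety reporting is descriptive; and the trial has stopped.

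Much of this stands. A reader might infer that the SAP explicitly runs safety by randomised arm. It does not: that follows only from combining SAP 6.2 with the ITT wording in Protocol 8.3. A reader might also infer that the plan expects misdosing, or that drug events have been counted under placebo. The documents support neither. Wrong treatment is one item in a list of PP exclusions, with no number attached and no report that it occurred. Multiplying an assumed dispensing error rate by the number of bags would not help, because the documents give no rate and some wrong bags would hold the subject's own treatment.

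The gap remains. The protocol's safety sentence says who is counted but not in which column, and SAP 6.2 names ITT outright. Descriptive tables are still planned. With the tests dropped, readers will rely on the raw counts by arm, where one misplaced subject is visible.

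**Conclusion.** The point holds as a gap in specification with a problematic default. SAP 6.2 departs from the safety basis in Protocol 8.3 without listing the change in SAP 5.4. The only grouping rule available for the set it names is the randomised one, and a foreseen type of deviation has no consequence for safety.

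The size is up to 4.3 points of incidence in an arm for each misdosed subject with an event, and zero if there was no misdosing. This assumes the planned 23 per arm and the default reading of ITT. Sample size, power and efficacy results are unaffected. The change is worth making because it is cheap and removes an avoidable doubt about the safety tables. The documents give no ground for saying that any reported safety result is wrong.

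**What to change.** In SAP 6.2, state that safety is analysed on all subjects who took at least one dose, as in Protocol 8.3, grouped by treatment actually received, and that efficacy ITT stays by randomised arm. Record the change in SAP 5.4, or in the clinical study report if the tables have already been run.

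List any subject who received a wrong bag, footnote that subject in the safety tables, and show each event's onset relative to the wrong bag. Do not move the whole subject to the highest dose received: a placebo subject with one wrong bag would then carry events from the placebo weeks into an active arm. State in advance the column in which a subject with mixed exposure is counted. If no subject was misdosed, one sentence saying so is enough.

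The cost is one derived actual-treatment variable. The bag label has fields for bag and subject number (Protocol 3.5.4.3), and dispense and return records are filed at site (Protocol 11.3). Neither document says that the bag number is in the study database, so it may have to be taken from those records. Safety denominators may differ slightly from the efficacy ITT denominators, which a table footnote can explain.

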6.3 Demographics and Other Baseline Characteristics

Demography and baseline characteristics will be listed by treatment group and analyzed between treatments to ensure comparability. Sample size, mean, median, standard deviation, IQR, range, maximum, and minimum will be summarized for continuous variables. For categorical variables, the frequency and percentage will be provided.

6.3.1 Demographic Data

Demographic data will consist of age (year), height (cm), weight (kg), BMI (kg/m²), gender and race.

$$\text{Age (years)} = \text{integer of } (\text{date of initial visit} - \text{date of birth}) / 365.25$$

$$\text{BMI (Kg/m}^2\text{)} = (\text{weight}) / (\text{height}/100)^2, \text{ rounds to first decimal place}$$

Demographic variables will be summarized by center and treatment group. Subjects' gender will be tabulated by treatment group.

6.3.2 ADHD History and Medical History

Frequency table of Diagnosis and Statistical Manual of Mental Disorders-V, text revision (DSM-V-TR) will be presented.

Frequency table of subject with medical history and current medical condition will be presented.

General medical history will be presented in incidence table and listed for each subject. Ongoing medical conditions will also be presented.

6.3.1 Concomitant Medications

Frequency table of subjects with pre-treatment and concomitant medications will be presented.

Pre-treatment medications are the medications taken before the first dosing of study drug, while concomitant medications are those taken during the treatment duration (from first dosing date of study drug to the day before exiting from study).

6.4 Baseline Determined

The data obtained before study drug administration in Visit 2 or Visit 1 (if no data at Visit 2) are set as baseline. For all other endpoint measurements, the last non-missing values before the first IP administration will be used as the baseline for the respective endpoints.

6.5 Study Treatment Administration

6.5.1 Treatment Compliance

Subjects' compliance (%) during the treatment period will be tabulated by center, and treatment and calculated according to the following formula:

$$= \frac{\text{Number of study medication actually took during the extent of exposure}}{\text{Number of study medication should be taken during the extent of exposure (\#)}} \times 100$$

= (number of study medication should be taken per day) * (extent of exposure, section 6.5.2)

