5.2.2 Part II.- Treatment Period (Visit 2~6)

Subjects who meet the eligibility criteria will be enrolled and take study drugs. At visits 2 to 5, each subject will be dispensed a supply of study drug sufficient for next 2-week treatment period. The subjects will be instructed to take one dose (i.e., two capsules) after a meal thrice daily. Drug compliance is important for the safety and efficacy evaluations. Study coordinator needs to make sure drug adherence of the subjects is at least

80% during the treatment period. Otherwise, study coordinator(s) must report a protocol deviation including lower than 80% compliance and over 100% compliance during the treatment period. At visits 2, 3, 4, 5 and 6, the safety and efficacy parameters will be evaluated by the following items. Baseline data will be collected before dosing study drug.

- Physical examination: skin, head, neck, eyes, ears, nose, throat, heart, lungs, abdomen (liver, spleen), neurological examination, lymph node and extremities.
- Vital sign: heart rate, blood pressure, body temperature
- ECG (Only at visit 6)
- Hematology: RBC, WBC, platelets, hematocrit, hemoglobin, prothrombin time (PT), partial thromboplastin time (aPTT). (Only at visit 2, 4 and 6)
- Blood chemistry: AST, ALT, LDH, total bilirubin, BUN, serum creatinine, free thyroxine (FT4), TSH, sodium, calcium, potassium, LDL, HDL, triglyceride, cholesterol. (Only at visit 2, 4 and 6)
- CAARS-S:S, CGI- -S (only for Visit 2), CGI- I (only for Visit 3 – 6), ADHD-RS-IV, E-SCT, C-SSRS and concomitant medication evaluation.
- AE/SAE evaluation
- Drug accountability

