6.5.2 Extent of Exposure

Extent of exposure (days) = date of last drug taken – date of first drug taken + 1

If the date of first drug taken is not available, the date when the drug was firstly dispensed will be used for calculation.

If the date of last drug taken is not available, the date will be replaced with that of the last drug return, previous drug taken, or previous drug return in order.

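### Compliance is counted only from first to last dose, so stopping the drug early cannot by itself fail the 80% per-protocol criterion

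*SAP*

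**What the plan says.** SAP 6.5.1 introduces compliance as a figure for the treatment period. Its numerator is "Number of study medication actually took during the extent of exposure" and its denominator is "Number of study medication should be taken during the extent of exposure". The denominator is then spelled out as the product ("number of study medication should be taken per day) * (extent of exposure, section 6.5.2"). SAP 6.5.2 supplies the missing term: "Extent of exposure (days) = date of last drug taken – date of first drug taken + 1". It adds a fallback: "If the date of last drug taken is not available, the date will be replaced with that of the last drug return", followed by earlier intake or return dates. No other compliance formula appears in either document.

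Protocol 5.2.2 sets the adherence target: "Study coordinator needs to make sure drug adherence of the subjects is at least" 80% over the treatment period, with lower values (and values above 100%) reported as deviations. Protocol 3.5.4.1 and 5.2 and SAP 5.2.2 all give treatment as three times daily for 56 days.

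The result feeds the PP set. The first PP condition in SAP 5.3.1 is "The drug compliance is at least 80" per cent. The second is completed data for the primary endpoint. The third is no protocol deviation, defined as an eligibility failure, a prohibited concomitant medication or a wrongly prescribed treatment. Protocol 8.3 has the same three conditions, with the deviation called major.

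**The concern.** The numerator and denominator both stop at the last dose. The score therefore measures how regularly a subject dosed while dosing, and says nothing about how much of the course was taken. A subject who gives up the drug after two weeks is not marked down for the six weeks that follow.

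A PP analysis is meant to show the result in subjects who were adequately treated. Here its treatment-adequacy condition cannot detect the most obvious form of inadequate treatment. The compliance table shares the weakness, and so does the mean daily dose in SAP 6.5.3, which uses the same denominator. SAP 6.5.2 defines the extent of exposure but states no summary of it, so the SAP text plans no other table in which a shortened course would show.

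**Working it through.** **Inputs.** One pack (2 capsules) three times daily for 56 days; bags of 42 packs plus 6 reserve, dispensed at Visits 2 to 5 (Protocol 3.5.4.1 and 3.5.4.2). PP threshold 80% (SAP 5.3.1). Visit window ±2 days (Protocol Table 15).

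**Reproducing the plan's figure.** 3 packs × 14 days = 42 packs per bag, as stated. Four bags give 4 × 42 = 168 = 3 × 56 packs, or 336 capsules.

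**The two formulas.** Let a subject stop after day *d*, having taken a fraction *f* of the packs due up to then.

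- SAP formula: 3*df* / 3*d* = *f*. The stopping day cancels out.
- Planned course: 3*df* / 168 = *f* × *d*/56.

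With full intake up to the stop (*f* = 1) and a known last-dose date:

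| Last dose on day | SAP 6.5.1 | Planned 56 days |
|---|---|---|
| 1 | 3/3 = 100% | 3/168 = 1.8% |
| 14 | 42/42 = 100% | 42/168 = 25.0% |
| 28 | 84/84 = 100% | 84/168 = 50.0% |
| 40 | 120/120 = 100% | 120/168 = 71.4% |
| 44 | 132/132 = 100% | 132/168 = 78.6% |
| 45 | 135/135 = 100% | 135/168 = 80.4% |

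The crossing point is 0.8 × 56 = 44.8 days, so the two rules disagree for every such stop before day 45.

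**When the score is not 100%.** If doses were missed before the stop, the SAP score is *f*. For a day-14 stop, *f* = 0.90 gives 90% and passes (0.90 × 14/56 = 22.5% of the planned course), while *f* = 0.75 gives 75% and fails.

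**When the last-dose date is missing.** The fallback date can lengthen the denominator. For a day-14 stop, an assumed return on day 28 gives 42/84 = 50.0%, a fail. An assumed return on day 15 gives 42/45 = 93.3%, a pass.

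**From the score to the PP set.** Passing the compliance condition is not enough; the other two conditions must also hold. Stopping the drug is not among the listed deviations, so the third does not catch it. The second is met by a subject who stops the drug but attends Visit 6, where SAP 6.6.1 evaluates response. For a subject who leaves before Visit 6, the answer depends on whether a value imputed by last observation carried forward (LOCF) counts as completed data. Neither document says.

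**The case against.** The strongest reply is that the SAP defines compliance and its definition governs. Protocol 5.2.2 gives no denominator and is an instruction to coordinators on adherence and deviation reporting. The PP definition in Protocol 8.3 gives only the 80% figure. On that view, a subject who passes the SAP formula is in the PP set correctly, and the on-drug ratio has the merit of separating missed doses from discontinuation. The documents also describe no schedule of visits off drug: Protocol 4.5 covers withdrawal from the trial, and Protocol 8.4 treats premature termination of therapy as a source of missing data. Many early stoppers would then lack Visit 6 and fail the second PP condition, if that condition means observed data. Protocol 8.4 also requires a listing of premature terminations with dates and reasons.

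Much of this stands as a limit on the point. A reader might infer that every early stopper scores 100% and enters the PP set. The documents do not support that: 100% needs full intake up to the stop and a known last-dose date, and PP entry needs two further conditions. A reader might also infer that adherence is overstated in every arm, but that holds only for arms with early stoppers.

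The reply does not rescue the formula. SAP 6.5.1 itself labels the result as compliance over the treatment period, and both documents set treatment at 56 days. Nothing rules out a subject who stops the drug and still attends Visit 6. A listing of terminations changes neither PP membership nor the compliance table.

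**Conclusion.** The point holds in a limited form. With a known last-dose date, early discontinuation cannot by itself fail the 80% criterion. An otherwise fully adherent subject who stops before day 45 passes, and can enter the PP set if the primary-endpoint data are complete and no listed deviation applies. The size per subject is as tabulated; the number of subjects cannot be derived from the documents. The day-45 boundary assumes that the treatment period means the planned 56 days, which is the natural reading, though Protocol 5.2.2 does not state it as a denominator.

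The consequence is confined to the PP efficacy summaries and the compliance table. SAP 6.2 rests the primary conclusion on ITT, and SAP 5.4 drops the between-arm tests after the trial was terminated. It would go too far to infer that the formula hides a real treatment effect or alters the trial's conclusion. Dilution of a PP difference is possible, but its size is unknown and no planned decision depends on it. The change is still worth making, because efficacy is still to be reported on the PP set and compliance is still to be tabulated by center and treatment.

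**What to change.** - For the PP criterion and the compliance table, set the denominator to 3 packs per day times the days from first dose to Visit 6, or times the planned 56 days if Visit 6 did not occur.
- State how those days are counted. Visit 6 date minus first-dose date gives 56 if the first dose is on the Visit 2 day and Visit 6 falls exactly at week 8.
- Keep the first-to-last-dose ratio as a descriptive dosing-intensity figure.
- State that an LOCF value does not count as completed data for the PP set.

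Neither single denominator works alone. A fixed 168 packs would score a fully adherent subject dosed for 58 days, within the visit window, at 174/168 = 103.6%, and Protocol 5.2.2 makes values above 100% a reportable deviation. With Visit 6 as the end point the same subject scores 174/174 = 100%. First dose to Visit 6 is undefined for a subject without Visit 6, hence the 56-day rule there.

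The cost is one formula and a few sentences. The 80% threshold does not change. The PP set may lose a few subjects. The SAP is dated April 25, 2024 and already refers to the interim result, so this would be a change made after that result was known. It should be documented as such, with PP results shown under both definitions.
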